4.4.7.1. EuroQol questionnaire (EQ-5D-3L)

The EQ-5D-3L is a two-part self-assessment questionnaire. The first part consists of five items covering five dimensions (mobility, self-care, usual activities, pain/discomfort, and anxiety/depression). Each dimension is measured by a three-point Likert scale (no problems, some problems and extreme problems). The second part is a vertical response scale (EQ-VAS) that has endpoints labelled “best imaginable health state” and “worst imaginable health state” anchored at 100 and 0, respectively.

A participant is classified into one of 243 distinct health states (each being referred to by a 5-digit code based on the responses to each dimension in the descriptive system, e.g., 11111 or 33333). EQ-5D-3L health states are converted to a single summary index by applying a formula that essentially attaches weights to each of the levels in each dimension. The formula is based on the valuation of EQ-5D health states from general population samples.

The EQ-5D-3L health state is converted to a health state value, using the value set for the United Kingdom as described in [Dolan, 1997]. EQ-5D-3L health state values summarize how good or bad health problems are on a scale anchored at 1 (full health) and 0 (state equivalent to dead). Health states considered worse than dead are given values <0.

Valid non-missing responses are required to all questions for a health state value to be assigned, if there is a missing or ambiguous response in any dimension the health state value will be set to missing.

Both parts of the EQ-5D-3L questionnaire will be summarized by visit up to Week 104. Data will be included in summaries regardless of treatment discontinuation or occurrence of any other intercurrent events.

4.5. Safety Analyses

The safety analyses will be based on the Safety population. Data up to Week 104 will be summarized for the Safety Population; where specified, additional displays will present information separately for participants enrolled in the study for 52 weeks only and for those in the Extended Treatment population. Extended Treatment population safety displays will be summarized based on actual treatment received for more than 50% of administrations. Data separated by time of onset (before and after Week 52) will be summarized for the Safety population where specified.

4.5.1. Extent of Exposure

IP is administered approximately every 4 weeks and each dose viewed as providing therapeutic coverage for 4 weeks (28 days). Duration of exposure in months is calculated based on the therapeutic coverage as follows:

$$\text{Duration of Exposure (months)} = (\text{IP Stop Date} - \text{IP Start Date} + 29) * 12 / 365.25$$

Patient years exposure is calculated as follows:

$$\text{Patient Years Exposure} = (\text{IP Stop Date} - \text{IP Start Date} + 29) / 365.25$$

If the IP start date is missing and there is evidence the participant received at least one dose of IP, the IP start date will be taken to be the date of randomization.

Randomized participants with no evidence of receiving at least one dose of IP will be shown as having zero months of exposure.

Exposure will be summarized by treatment arm for all subjects in the safety population, for participants enrolled for 52 weeks only and for those in the Extended Treatment population. A listing of exposure data will also be produced.

4.5.2. Adverse Events

Summaries of adverse events (AEs), serious adverse events (SAEs) and other significant AEs will be based on GSK Core Data Standards. Summaries for the Safety Population will include AEs experienced up to Week 104. For on-treatment AEs, SAEs, common AEs and AESIs, separate displays will be produced for participants enrolled for 52 weeks only and for those in the Extended Treatment Population. Summaries of AEs, SAEs and AESIs will be produced by time of onset (before and after Week 52) where specified. Where applicable, exposure-adjusted rates will be included in summaries.

Adverse events will be coded using the standard Medical Dictionary for Regulatory Affairs (MedDRA dictionary), with the maximum severity of each AE determined by the investigator (as mild, moderate, or severe). Unless otherwise specified, summaries are presented in descending order of frequency by system organ class and preferred term.

An overview summary of AEs will be generated, including counts and percentages of participants with any AE, AEs related to study treatment, AEs leading to permanent

discontinuation of study treatment, AEs leading to withdrawal from the study, SAEs, SAEs related to study treatment, fatal SAEs, and fatal SAEs related to study treatment.

Adverse events will be determined to be pre, on or post-treatment as described in Section 6.2.3.4. The number and percentage of participants experiencing AEs during the on-treatment and post-treatment periods will be summarized separately. Additionally, summaries of the number and percentage of participants with any on-treatment AEs by maximum severity will be produced. If an adverse event severity is missing, the severity will be populated as 'UNKNOWN'.

A separate summary will be provided for drug-related AEs. The summary will include events with the relationship to study intervention of 'Yes' or missing. On-treatment drug-related AEs will also be reported by maximum severity.

Summaries of SAEs, fatal and non-fatal SAEs, common AEs defined as $\geq 3\%$ (prior to rounding), AEs leading to discontinuation of study treatment, AEs leading to withdrawal from study, AEs reported on the day of dosing, and AEs by highest post-baseline anti-drug antibody result will be reported separately.

Adverse events of pneumonia will be summarized, these will be identified through matching of collected adverse event preferred terms with those from the Infective Pneumonia SMQ (narrow terms) prior to unblinding based on the latest version of the MedDRA dictionary available at the time of database lock for this study.

4.5.2.1. Adverse Events of Special Interest

Adverse events of special interest (AESIs) are adverse events which are to be closely monitored as the development of mepolizumab progresses. AESIs in the mepolizumab clinical development program are described in the mepolizumab BRMP/DRMP [GSK Document Number; 2020N436792]. The methods by which these events will be identified within this study reporting are detailed in Section 6.4.

AESIs of anaphylaxis reactions, systemic reactions, and local injection site reactions are collected via targeted eCRF. The AESIs of potential opportunistic infections, malignancies, serious CVT events and serious ischemic events will be identified from a list of relevant preferred terms maintained within a project level reference dataset; created based on the latest version of the MedDRA dictionary available at the time of database lock for this study.

Separate summary tables showing the number and percent of participants with each type of AESI, broken down by preferred term will be created. These summaries will be reported as part of the standard AE/SAE tables for the AESIs of infections, serious infections, neoplasms, cardiac disorders and serious cardiac disorders.

The relative risk and risk difference of each AESI between mepolizumab and placebo will be presented with 95% confidence intervals. A forest plot displaying the relative risk with 95% CI will also be produced.

For each AESI a profile summary table will be produced containing information on event characteristics including, but not be limited to, the number of participants with the AESI, the number of occurrences of the AESI, the number of participants with a serious event or a drug related event, maximum severity, outcome and action taken. Separate listings will be provided of participants with systemic reactions identified by the investigator as meeting the criteria for anaphylaxis, systemic reactions categorized as allergic (type I hypersensitivity), systemic reactions categorized as other, and all other AESIs.

4.5.2.2. Adjudication of Adverse Events and MACE

External adjudication of all serious cases will be completed in a blinded manner by case-based adjudication, with classification of primary cause of death for fatal cases or a classification of the primary event in the non-fatal cases.

For all cases with a fatal SAE, the Clinical Endpoint Committee (CEC) members will indicate the primary cause of death. Additionally, the CEC members will determine if the death is associated with the participant's known COPD.

For all non-fatal SAE cases, the CEC members will be asked to categorize the primary SAE. If there is more than one event for a patient in the same SAE report, the primary event will be the adverse event of greatest medical significance.

The categories will be as follows:

- Cardiovascular (sudden death (for fatal events only), myocardial infarction/ischemic heart disease, congestive heart failure, stroke or other cardiovascular cause)
 - Stroke is further categorized as hemorrhagic, thromboembolic or indeterminate
- Respiratory (COPD exacerbation with or without evidence of pneumonia, pneumonia/respiratory tract infection without COPD exacerbation, pulmonary embolism, other respiratory cause)
- Cancer (lung, breast, colorectal, unknown primary, other)
- Other
- Unknown (inadequate information or indeterminate).

Adjudication of all MACE (cardiovascular death, non-fatal acute MI, non-fatal acute stroke) will be completed by event-based adjudication in a blinded manner. MACE will be adjudicated based on criteria given in the CEC Charter Version3. Serious and nonserious events potentially representing acute MI and acute stroke will be identified for adjudication as events with a PT matching the list of PTs in pre-selected MedDRA SMQs.

Myocardial infarctions will be classified as:

- ST segment elevation myocardial infarction (STEMI)
- Non-ST segment elevation myocardial infarction (NSTEMI)
- Myocardial infarction, type (i.e., STEMI or NSTEMI) unknown

Strokes will be classified as intracerebral hemorrhage, subarachnoid hemorrhage, ischaemic (non-hemorrhagic) or undetermined. Events considered to not meet the charter definition of stroke but consistent with extra-axial hemorrhage will be classified as subdural, extradural or other.

All fatal events will be reviewed for adjudication of MACE component cardiovascular death. Cardiovascular deaths will be classified as acute MI (with sub-classifications as above), sudden cardiac death, heart failure, stroke (with sub-classifications as for stroke events above), cardiovascular procedure (with sub-classifications of PCI, CABG or other), cardiovascular hemorrhage (with sub-classifications of subdural, extradural, ruptured aortic aneurysm or other) or other cardiovascular cause (with sub-classifications of peripheral artery disease or other).

4.5.2.2.1. Time to first adjudicated MACE

Time to first adjudicated MACE will be analyzed and summarized. This will be determined as the number of days from the date of first dose to the date of the first adjudicated MACE:

Time to first adj. MACE = date of first adj. MACE – date of first dose +1

Partial dates related to adjudicated MACE will be queried, in the event the full start date cannot be determined, imputation as described in Section 6.2.7 will be applied.

The variable of interest is the time to first adjudicated MACE. For analyses of time to first ‘on- and post-treatment’ MACE, participants who complete the study or withdraw from the study prior to completion without experiencing a MACE will be censored at their respective completion or study withdrawal date. For analyses of time to first ‘on-treatment’ MACE, participants who do not experience a MACE prior to the end of their on-treatment period, as defined in Section 6.2.3.3 will be censored at their end of IP date + 28 days.

The analysis will be carried out using a Cox proportional hazards model with treatment group as the only categorical covariate. The model checking & diagnostics will follow the same strategy as outlined in Section 4.3.1.2. The number of participants with an event, the number censored due to study withdrawal and at study completion will be presented by treatment arm. The hazard ratio with corresponding 95% CI and p-value from the Cox proportional hazards model will be presented.

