8.3.1. Time Period and Frequency for Collecting AE and SAE Information

- **China only:** In China, all SAEs will be recorded from the time the consent form is signed until the Exit Visit/Study Withdrawal Visit at the time points specified in the SoA (Section 1.3).

- All SAEs will be collected from the start of study intervention until the Exit Visit/Study Withdrawal Visit at the time points specified in the SoA (Section 1.3). However, any SAEs assessed as related to study participation (e.g., study intervention, protocol-mandated procedures, invasive tests, or change in existing therapy) or related to any GSK product will be recorded from the time a participant consents to participate in the study.
- All AEs will be collected from the start of study intervention until the Exit Visit/Study withdrawal visit at the time points specified in the SoA (Section 1.3). Medical occurrences that begin before the start of intervention product but after obtaining informed consent will be recorded on the Medical History/Current Medical Conditions section of the CRF not the AE section.
- All SAEs will be recorded and reported to the sponsor or designee immediately and under no circumstance should this exceed 24 hrs, as indicated in Appendix 4. The Investigator will submit any updated SAE data to the sponsor within 24 hours of it being available.
- Investigators are not obligated to actively seek AEs or SAEs after the conclusion of the study participation. However, if the Investigator learns of any SAE, including a death, at any time after a participant has been discharged from the study, and he/she considers the event to be reasonably related to the intervention product or study participation, the Investigator must promptly notify the sponsor.

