6.2.3.1. Treatment Phases for Exacerbations

Treatment State	Definition
Pre-Treatment	Event start date < IP start date
On-Treatment	For participants who did not prematurely withdraw from IP: Event onset date is on/after IP start date & on/before the end of analysis period. (IP Start Date ≤ Event Start Date ≤ end of analysis period) For participants who prematurely withdrew from IP: Event onset date is on/after IP start date & on/before earlier of the IP stop date +28 days/end of analysis period. (IP Start Date ≤ Event Start Date ≤ earlier of IP Stop Date + 28 days/end of analysis period)
Off-Treatment	Event onset date is after IP stop date +28 days and on/before the end of analysis period. (IP Stop Date + 28 days < Event Start Date ≤ end of analysis period)
Post-treatment	Event onset date is after the end of analysis period. (Event Start Date > end of analysis period)
Duration of Exacerbation (Days)	Event resolution date – Event onset date + 1

Treatment State	Definition
	Analysis period as defined in Section 6.2.2 If the IP stop date is missing or the event start date is partial/missing then unless there is evidence to the contrary the event will be considered to be On-Treatment (see Section 6.2.7)

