6.2.3.3. Treatment Phases for Visit Based Safety Assessments

Treatment State	Definition
Pre-Treatment	Assessment Date \leq IP Start Date
On-Treatment	IP Start Date < Assessment Date \leq IP Stop Date +28 days
Post -Treatment	Assessment Date > IP Stop Date + 28 days

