6.2.3.4. Treatment Phases for Adverse Events

Treatment State	Definition
Pre-Treatment	Event Start Date < IP Start Date
On-Treatment	Event onset date is on/after IP start date & on/before IP stop date +28 days. (IP Start Date \leq Event Start Date \leq IP Stop Date + 28 days)
Post-Treatment	Event onset date is after the IP stop date + 28 days. (Event Start Date > IP Stop Date + 28 days)
Onset Time Since 1 st Dose (Days)	If event onset date < IP start date = IP start date - Event onset date If event onset date \geq IP start date = Event onset date - IP start date + 1 Missing otherwise.

Treatment State	Definition
Duration (Days)	Event resolution date – Event onset date + 1

NOTES:

If the IP stop date is missing or the event start date is partial/missing then unless there is evidence to the contrary the event will be considered to be On-Treatment (see Section 6.2.7).

Where time of event is recorded, the time of event and time of first dose will be considered to differentiate between Pre-treatment and On-treatment events.

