	Partial End Date (for Adverse Events)	'28/29/30/31' will be used for a missing day (dependent on the month and year) and 'Dec' will be used for a missing month. If this results in a date after the study treatment stop date +28 days, then the study treatment stop date + 28 days will be used.
	Completely missing start/end date	No imputation is applied.
Concomitant Medications/ Medical History	Partial dates for any concomitant medications or medical history conditions recorded in the CRF will be imputed using the following convention:	
	Partial Start Date	'01' will be used for the day and 'Jan' will be used for the month.
	Partial End Date	'28/29/30/31' will be used for the day (dependent on the month and year) and 'Dec' will be used for the month.
	Completely missing start/end date	No imputation is applied.

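### Two SAP safety date rules ignore when observation ended: on-treatment MACE follow-up can run past it, and partial AE end dates can be imputed before onset

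*SAP*

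**What the plan says.** **MACE.** SAP 4.5.2.2.1 plans two versions of time to first adjudicated MACE. In the combined on- and post-treatment version, event-free participants "will be censored at their respective completion or study withdrawal date". In the on-treatment version, those with no MACE before their on-treatment period ends "will be censored at their end of IP date + 28 days". The period is taken from SAP 6.2.3.3, where the post-treatment phase begins at "Assessment Date > IP Stop Date + 28 days". Neither section limits this to the time a participant was observed.

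Protocol 8.3.1 sets the observation period: "All AEs will be collected from the start of study intervention until the Exit Visit/Study withdrawal visit". The Exit Visit is scheduled 4 weeks after the last dose (Protocol 4.1), and every visit has a ±7-day window (Protocol 1.3.1).

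For exacerbations, the on-treatment phase of a participant who stops IP early ends at the "earlier of IP Stop Date + 28 days/end of analysis period" (SAP 6.2.3.1). SAP 6.2.2.2 limits time at risk in the same way.

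**Partial AE dates.** SAP 6.2.7 fills a missing end day with the last day of the month and a missing end month with December. If the result is later than 28 days after treatment stopped, "then the study treatment stop date + 28 days will be used". SAP 6.2.3.4 makes an AE on-treatment when "Event onset date is on/after IP start date & on/before IP stop date +28 days" and post-treatment when onset is later. It defines duration as resolution minus onset plus 1. The exacerbation row of 6.2.7 caps at the exit visit date instead.

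**The concern.** A censoring time should be the last time at which an event could have been recorded. The on-treatment MACE rule fixes it from the last dose alone, so a person can stay in the risk set after death or departure. On-treatment follow-up can then be longer than the same person's follow-up in the companion analysis that is meant to contain it. The section also promises counts of participants censored for study withdrawal and at study completion, which are categories the on-treatment rule does not produce.

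The AE rule applies an on-treatment limit to events that by definition start after that limit. It affects participants who stop IP and remain under follow-up, whom the protocol tries to retain.

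Cardiovascular effects are a named potential risk (Protocol 2.3.1), and the time-to-first-MACE analysis was added in SAP Amendment 1. Its risk sets, and the AE dates beside it, should be right by construction.

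**Working it through.** The documents give no numerical result for either rule, so there is no stated figure to reproduce. The check is date arithmetic on the rules.

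**Rule 1: on-treatment MACE censoring**

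Overrun = max(0, IP stop + 28 − last day observed).

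- *Exit on schedule:* last dose day 336, exit day 364. Gap 28 days, overrun 0.
- *Early exit, both visits in window:* shortest gap (364 − 7) − (336 + 7) = 14 days; longest (364 + 7) − (336 − 7) = 42 days. Overrun is therefore 0 to 14 days.
- *Non-cardiovascular death or loss soon after a dose:* 3 days after the dose, the overrun is 28 − 3 = 25 days. On the day of the dose it is 28 days, the maximum. A cardiovascular death on treatment is itself a MACE, so it does not arise here.

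Size as a share of 364 days of follow-up per person:

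| Source | Assumption (not in the documents) | Calculation | Excess |
|---|---|---|---|
| Death or early loss, low | 1% of participants, mean overrun 14 days | 0.01 × 14 / 364 | 0.04% |
| Death or early loss, high | 5.5%, mean overrun 14 days | 0.055 × 14 / 364 | 0.21% |
| Death or early loss, ceiling | 5.5%, all at 28 days | 0.055 × 28 / 364 | 0.42% |
| Early exit | all day pairs in the two windows equally likely | mean Σk(15 − k)/225, k = 1 to 14, = 560/225 = 2.49 days; 2.49 / 364 | 0.68% |

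The 5.5% borrows the missing patient-years figure from the sample-size section; the documents give no expected share of deaths. High case plus early exit: 0.21% + 0.68% = 0.89%. Ceiling: 0.42% + 0.68% = 1.10%. With censoring at the earliest of the relevant dates, the overrun is 0.

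**Rule 2: partial AE end dates**

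For a post-treatment AE with a partial end date:

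1. The imputed date is the last day of the month or year, so it is on or after the true end.
2. The true end is on or after onset.
3. Onset is after IP stop + 28 (SAP 6.2.3.4).

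The imputed date therefore always exceeds the cap, the cap always applies, and the assigned end always precedes onset. For onset at IP stop + d, with d ≥ 29, duration = (28 − d) + 1 = 29 − d: 0 at d = 29, and one day lower for each later day. Enumerating 155,184 combinations of stop date, onset, true length and missing date part agrees: all ended before onset.

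- *Post-treatment example:* IP stop 1 March 2022, onset 10 June 2022, end recorded as June 2022. Imputed 30 June, capped to 29 March. Duration −73 + 1 = −72 days.
- *On-treatment example:* same stop date, onset 20 March, end recorded as June 2022. Capped to 29 March, duration 10 days, although the event lasted at least to 1 June (74 days).

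With the cap at the Exit Visit or study withdrawal date, the end is never before onset for any AE starting on or before that date.

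**The case against.** The best defence is that IP stop + 28 days is a deliberate safety convention. SAP 4.5.1 treats each dose as giving 28 days of therapeutic coverage and computes exposure without a cap, and the MACE rule matches it. The exacerbation comparator is an efficacy analysis in which time is the model offset. A MACE analysis censored at completion or withdrawal is also planned. In a Cox model, extra tail time matters only if another participant's MACE falls at that same study time. When IP and study participation stop together, the withdrawal visit is due 4 weeks after IP discontinuation (Protocol 1.3.1, footnote c), so many withdrawals cause no overrun. On AEs, phase and incidence depend on onset, listings show partial dates as captured, and the summaries named in SAP 4.5.2 do not mention duration.

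Most of this stands as an argument about size. It does not make the rules right. A coverage convention defines exposure, not observation, and cannot supply event-free days after death. The negative durations have no defence.

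Three stronger readings are tempting but unsupported:

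- *A MACE on the day of first dose becomes pre-treatment.* A reader might infer this because SAP 6.2.3.3 starts the on-treatment phase at "IP Start Date < Assessment Date". But 4.5.2.2.1 uses that section only for the end of the period, which is the same in 6.2.3.4, and sets its own clock: MACE date minus first-dose date plus 1, which makes the first-dose day Day 1.
- *The rule lowers MACE rates.* The section reports counts, a hazard ratio, a confidence interval and a p-value, but no person-time rate.
- *About half of completers have wrong risk time.* That comes from spreading exits evenly over days 21 to 35 after the last dose (7/15 = 47%). The documents give no such distribution and schedule exit at 28 days.

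**Conclusion.** Both rules are wrong as written, and both faults are minor.

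The on-treatment MACE rule can extend follow-up beyond observation by up to 28 days per person. The total is about 1% of person-time or less if 1% to 5.5% of participants end early and visit timing is uniform within the windows, neither of which the documents state. The expected effect on the hazard ratio is very small, and bias between arms would need early endings to differ by arm. That follow-up can exceed the companion analysis follows directly for withdrawals and early exits. For deaths it assumes that death is recorded as study withdrawal, since neither rule names it.

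The partial-date rule fails for every post-treatment AE with an imputed end date and truncates some on-treatment AEs. The documents give no count of partial dates, so the number affected is unknown. Only derived end dates and durations change. No primary, secondary or AE-incidence result is touched.

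**What to change.** 1. **SAP 4.5.2.2.1:** censor on-treatment MACE at the earliest of IP stop + 28 days, death, study withdrawal and study completion/Exit Visit. Align the reported censoring categories with this. For tidiness, cite 6.2.3.4 (adverse events) instead of 6.2.3.3 (visit-based assessments); no censoring date changes as a result.
2. **SAP 6.2.7, AE end-date row:** cap the imputed date at the Exit Visit or study withdrawal date, and never set it before the AE start date. The floor is needed because Protocol 8.3.1 allows related SAEs to be reported after discharge.

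The cost is a few words in the SAP and two derivation lines. No new data are needed.
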